4.1 Main outcome

Successful decanulation is defined as maintenance of spontaneous ventilation in the absence of recanulation, acute use of non-invasive ventilation (NIV) or death within 48 hours.

Factors potentially associated with successful decanulation will be collected prospectively:

- Severity factors related to the ICU stay:

o Total number of oro-tracheal intubations ;

o Number of days on mechanical ventilation;

o Curarisation or not with duration

o Whether or not prone sessions were performed with duration;

o Whether or not ECMO was used as a back-up;

o Number of pneumopathies acquired under mechanical ventilation;

o IGS2 ;

- Ventilatory factors :

o Number of failed extubations before tracheostomy in the ICU;

o Duration of mechanical ventilation before tracheostomy in the ICU (days);

o Type of tracheostomy used: percutaneous or surgical;

o Time to first attempt at Difficult-to-Wean Unit de-ventilation (days);

o Time to 24-hour at Difficult-to-Wean Unit de-ventilation (days);

o Time from 24-hour deventilation to successful DIFFICULT-TO-WEAN UNIT decanulation (days);

o Number of ventilator-associated lung diseases (VAPs) in at Difficult-to-Wean Unit;

- Respiratory factors:

o Ultrasound lung ventilation score on admission to at Difficult-to-Wean Unit;

o Diaphragmatic dysfunction on admission to at Difficult-to-Wean Unit;

o Bronchial fibroscopy abnormalities prior to decanulation;

- Extra-respiratory factors:

o Confusional state on admission to at Difficult-to-Wean Unit (CAM-ICU, Appendix 1);

o Existing swallowing disorders (assessed after 6 hours of ventilation) by the modified Cowling swallowing score (18);

o Oral status on admission to at Difficult-to-Wean Unit (normal, moderately impaired, dilapidated, no teeth);

o ICU-Acquired muscle weakness (MRC score) on admission to at Difficult-to-Wean Unit;

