7.7 Decanulation decision

The decision to decanulate follows a progressive de-ventilation and assessment protocol based on respiratory and extra-respiratory criteria:

Respiratory criteria :

- Patient under mechanical ventilation 24 hours a day: the tracheostomy cannula is a nonwindowed or a windowed cannula with a low pressure cuff of the Silhey® LPC, Bivona® Mid-Range Air Cuf or Portex® Blue-Line Ultra type; allowing to limit the risks of tracheal lesions due to the cuff;

- Patient under mechanical ventilation <18h/24h or dislocated > 6h/24h (with the cuff of the tracheostomy cannula deflated): the cannula is changed for a non fenestrated high pressure cuffed cannula such as Bivona® TTS. This type of cannula is with a plated silicone cuff and is very well tolerated and facilitates speech therapy exercises. The size of the tracheostomy cannula is sometimes reduced to facilitate the exercises but this is not consensual and is more a matter of practice specific to each department.

- Patient discharged during the day: generally 8am-6pm, then progressive lengthening of the time before nocturnal reventilation (plateau at 8pm-10pm-00am).

- Patients discharged during the day and early evening: this discharging is continued throughout the night. Complete 24-hour de-ventilation is recorded when the patient is de-ventilated for 48 hours without the need for re-ventilation.

- Patient is deventilated 24 hours a day: the next step consists of placing a plug over the tracheostomy orifice. Thus, the patient's "classical" respiratory tract is used and the patient is in a respiratory situation equivalent to a patient without a tracheostomy tube.

Extra-respiratory criteria:

After 48 hours with the cannula plugged, in the absence of a respiratory event, the patient is considered decanulable. Various assessments are carried out to ensure that there are no potentially negative predictive factors:

- Speech therapy: pharyngolaryngeal oedema is assessed by phonation exercises. These exercises can also be used to assess vocal cord and/or glossal damage. Swallowing of liquids and solids is tested.

- Physiotherapy: neuromuscular and diaphragmatic function (MRC score, ultrasound) are assessed.

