9.3 End of research visit

The end-of-research visit will be carried out when the patient is discharged from the DIFFICULT-TO-WEAN UNIT. The necessary additional information will be collected from the patient's computerised medical record.

The variables collected are :

- Time to spontaneous ventilation (days);
- Time to 1st attempt at de-ventilation (days);
- Time to 24-hour de-ventilation (days);
- Time between 24-hour deventilation and successful final decanulation (days);
- Number of decanulations performed;
- Performance of a decanulation bronchial fibroscopy (yes/no) with abnormalities observed:
 - o pharyngeal oedema ;
 - o unilateral vocal cord paralysis;
 - o Bilateral vocal cord paralysis;
 - o unilateral arytenoid palsy
 - o bilateral arytenoid palsy;
 - o Tracheal ring fracture;
 - o No abnormality observed.
- Number of VAPs in DIFFICULT-TO-WEAN UNIT ;
- Total duration of antibiotic therapy (days) ;
- MRC score;
- Presence of undernutrition (severe/moderate/minimal/no);
- Presence of a nasogastric tube (yes/no);
- Presence of a percutaneous gastrostomy (yes/no);
- Oral feeding resumed (yes/no);
- Mode of discharge (return to intensive care, return home, death).

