10.3 Main objective

Patients will be classified into 2 groups: success or failure of decanulation. The variables collected will be compared between the 2 groups by the appropriate tests according to the type of variables (quantitative or qualitative) and their distribution. The results of these comparisons will be used to select the variables showing a difference between the 2 groups (p < 0.20) for inclusion in the multivariate logistic regression. (24)(25)

The previously selected ultrasound variables will be included in the model predicting the success of decanulation. Multiple logistic regression with variable selection using the Akaike information criterion (AIC) method will be used. The presence of multicollinearity between variables will also be investigated and the variable eliminated if necessary.

11 Expected results in terms of scientific and professional advances

This study will determine the factors contributing to the success of decanulation in patients admitted to DIFFICULT-TO-WEAN UNIT after a prolonged ICU stay. The evaluation of these success factors will provide data that is still lacking due to the lack of literature in specialised post-resuscitation ventilatory weaning facilities.

This information may be useful in the post-resuscitation follow-up and in the prioritisation or not of early rehabilitation in these patients.

12 Expected benefits and risks for patients

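### The unit VAP factor is a raw count to discharge, with no ventilated-time denominator and no cut-off at the outcome, so it is likely to be confounded by ventilated exposure

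*Combined protocol and SAP*

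**What the plan says.** Section 4.1 gives the unit factor as "Number of ventilator-associated lung diseases (VAPs) in at Difficult-to-Wean Unit". Section 9.3 collects it as "Number of VAPs in DIFFICULT-TO-WEAN UNIT", and the timing is that of the final visit: "The end-of-research visit will be carried out when the patient is discharged from the DIFFICULT-TO-WEAN UNIT". The count therefore covers the whole unit stay.

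Section 10.3 sets up the comparison: "Patients will be classified into 2 groups: success or failure of decanulation". It continues: "The variables collected will be compared between the 2 groups by the appropriate tests according to the type of variables". Variables with p < 0.20 go forward to a logistic regression with AIC selection. Sections 4.1, 9.3, 10.2 and 10.3 give no rate, offset or exposure window for the VAP count.

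Section 7.7 sets the steps before the cannula is removed. First: "Complete 24-hour de-ventilation is recorded when the patient is de-ventilated for 48 hours without the need for re-ventilation". Then: "After 48 hours with the cannula plugged, in the absence of a respiratory event, the patient is considered decanulable". Section 4.1 adds 48 hours after removal without recanulation, acute NIV or death before a decanulation counts as a success.

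**The concern.** A ventilator-associated event can only arise while the patient is ventilated. If the two outcome groups spend different numbers of days on the ventilator, their raw counts differ even when incidence per ventilated day is identical. The comparison then partly measures ventilated time, which is closely tied to the outcome.

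There is also a timing problem. The count runs to discharge, and section 9.3 allows for more than one decanulation per patient. A VAP acquired on re-ventilation after a failed decanulation would be counted as a factor for a failure that came before it.

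At stake is a false determinant in the main analysis, occupying one of the six model places planned in section 10.1.

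**Working it through.** **The plan's own figure.** Section 10.1: 6 variables × 10 events ÷ 0.60 success = 100 patients. This reproduces the stated number and implies 60 successes and 40 failures.

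**Who the failures are.** Section 10.3 does not say where never-decanulated patients go. Section 4.2 takes the success proportion over all included patients, and section 1 puts failure after decanulation at 2 to 25%. If that range applied here, with 60 successes:
- at 25%: 60 ÷ 0.75 = 80 decanulated, 20 failed after removal, 20 never decanulated;
- at 2%: 60 ÷ 0.98 ≈ 61 decanulated, about 1 failed after removal, about 39 never decanulated.

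So 20 to 39 of the 40 failures would be patients never decanulated. This is an inference; the plan does not state it.

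**Off-ventilator time in a success.** 48 h de-ventilated + 48 h plugged + 48 h after removal = 144 h = 6 days. If both groups stayed 30 days (section 6.3 gives one month, as an overall average only), a success would have at most 30 − 6 = 24 ventilated days, against 30 for a patient never taken off the ventilator. At an assumed 10 VAPs per 1000 ventilated days, the expected counts are 0.01 × 24 = 0.24 and 0.01 × 30 = 0.30 per patient, with no difference in incidence.

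**Simulation.** Inputs: 60 successes, 40 failures, Poisson counts, the same incidence per ventilated day in both groups, raw counts compared by Wilcoxon test. The documents give neither VAP incidence nor ventilated days by group, so both are assumptions.

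With a fixed number of ventilated days per group and 10 to 20 VAPs per 1000 days, repeated runs gave p < 0.20 in:
- about 25–31% at 24 versus 30 days (p < 0.05 in about 8–12%);
- 59–80% at 15 versus 30 days.

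With ventilated days varying between patients (gamma, shape 4) and 5 to 20 VAPs per 1000 days:

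| Mean ventilated days, success vs failure | p < 0.20 | p < 0.05 | Apparent direction |
|---|---|---|---|
| 10 vs 30 | 66–94% | 36–82% | towards failure |
| 15 vs 30 | 46–75% | 21–51% | towards failure |
| 20 vs 30 | 32–49% | 12–24% | towards failure |
| 15 vs 15 | 19–22% | about 5% | none |
| 15 vs half 30, half 8 | 24–26% | 7–8% | slight, towards failure |
| 20 vs 10 | 35–64% | 10–37% | towards success |
| Nominal | 20% | 5% | |

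At 10 per 1000, the median odds ratio for failure per VAP from a logistic model on the raw count was 1.47 (20 vs 30 days), 1.95 (15 vs 30) and 2.92 (10 vs 30), although VAP had no effect in the simulated data.

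**After the change.** Comparing VAPs per ventilated day (an exact conditional test in the simulation) gave p < 0.20 in 13–19% and p < 0.05 in 2–5% across all six scenarios, at or below nominal.

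**The case against.** Several stronger readings are tempting, and the documents do not support them.

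- **Successes have fewer ventilated days by rule.** Section 7.7 fixes a sequence, not a total. Patients who fail after removal have passed through the same steps. Failures can also leave early by death or transfer back to an ICU (section 9.3), and a patient can be fully de-ventilated yet not decanulated for swallowing or laryngeal reasons.
- **The ratio of ventilated days is at most 24 ÷ 30 = 0.80.** This holds only if both groups stay 30 days. With unequal stays it can exceed 1, as in the 20 versus 10 scenario.
- **The direction is known.** The table shows the bias disappearing with equal exposure and reversing with early exits.
- **The ICU count, "Number of pneumopathies acquired under mechanical ventilation", has the same defect.** The unit's de-ventilation steps cannot shorten ICU exposure, since every included patient arrives ventilated. Days on ventilation in the ICU are already a candidate factor in section 4.1.

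It can also be said that the plan partly covers the point, because time to 24-hour de-ventilation is itself a candidate factor. That helps little: AIC need not retain it, and patients never de-ventilated have no value for it. Duration of invasive ventilation appears in section 4.2 but is not tied to the VAP count.

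Forcing ventilated days into the logistic model is another tempting answer. If a VAP delays weaning, ventilated time lies on its causal path. In a simulation where each VAP truly added 7 days (assumed), the odds ratio fell from 3.2–3.4 to 1.5–1.6 with the term included, although part of the higher figure was itself artefact. The adjustment is debatable and is not recommended here.

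What stands is that the large percentages rest on assumed ventilated days. The scenario closest to the plan's figures shows only a modest excess.

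**Conclusion.** The point holds as a likely confounding by ventilated exposure, together with a missing cut-off at the outcome. It probably acts towards failure if never-decanulated patients are classed as failures. It can vanish or reverse if failures mostly exit early, so neither its direction nor its size can be read off the plan. In either direction, the raw-count comparison cannot be interpreted as an effect of VAP.

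With equal incidence, the excess over the nominal 20% screening rate runs from small (about 25–31% at 24 versus 30 days) to large (59–80% at 15 versus 30 days). Both figures assume 10 to 20 VAPs per 1000 ventilated days, and the first also assumes equal 30-day stays.

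Priority is modest. Section 4.1 lists 7 + 7 + 3 + 4 = 21 candidate factors, and this affects one of them.

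**What to change.** In section 10.3:

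1. Count only unit VAPs that occur before the first decanulation, or before unit exit if there is none.
2. Replace the raw-count comparison with VAPs per invasively ventilated day over the same period, by Poisson or negative binomial regression with log ventilated days as offset.
3. Do not enter the raw discharge count in the logistic model.
4. State whether never-decanulated patients, including those who die or return to an ICU, are classed as failures, because the interpretation depends on it.

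**Cost.** The date of each VAP, the date of first decanulation and the ventilated days up to that date must be recorded. Section 9.3 lists none of these, and the duration in section 4.2 covers the whole hospitalisation. Because ventilation is withdrawn by hours per day, a ventilated day needs a definition for partial-day ventilation.

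**Limits.** The rate is less precise in patients with few ventilated days. It compares VAP incidence by outcome group, so it does not itself give an adjusted odds ratio for success. It does not remove reverse causation, since a VAP can itself prolong ventilation.

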8.3 Diaphragm ultrasound

Ultrasound of the diaphragm will assess the excursion (mobility) and thickening of the diaphragm on the right and left. The procedure is described in Appendix 8. Each measurement will be repeated 3 times, the best one will be retained.

9 Conduct of the study

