10.1 Number of subjects needed

The calculation of the number of subjects required is based on the number of explanatory variables to be included in the multiple logistic regression model to determine the factors associated with successful decanulation. The "1 variable per 10 events" rule is applied. (23) We anticipate 6 variables to be included in the final multivariate predictive model, after selection of variables in univariate analysis, based on an estimated 60% success of decanulation (retrospective estimate on data available in the department), i.e. a necessary number of subjects of 100 patients.

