15.8 Appendix 8: Diaphragmatic ultrasound

When assessing the diaphragm in mechanically ventilated patients, and if the patient's respiratory status permits, the ventilator parameters are changed by the physician: AI = 7 cmH20 and PEEP = 0 cmH20, to reflect spontaneous ventilation conditions.

Diaphragm excursion: anterior subcostal route: The convex probe is placed in the anterior subcostal route, between the anterior axillary line and the mid-clavicular line: B mode is initially used to obtain the best visual approach. After this identification, the measurement of the diaphragm excursion is carried out in TM mode: during inspiration the diaphragm moves towards the probe and away from it during expiration. The excursion is equal to the distance measured between inspiration and expiration (maximum effort required from the patient). An excursion < 2.5 cm (LerolleChest, 2009) indicates a diaphragm dysfunction.

Thickening of the diaphragm: Examination modalities: The probe is placed in an intercostal space, between the median and anterior axillary line, 0.5cm to 2cm below the costophrenic sinus. In B-mode, the diaphragm appears as a hypoechoic structure between two hyperechoic layers: the pleura (outer layer) and the peritoneum (inner layer). The thickening fraction (TF) is measured in B mode according to the following formula: TF (%) = [(end-inspiratory thickness - end-expiratory thickness]/ end-expiratory thickness] x 100. The patient is asked to perform maximum inspiration and expiration. A TF < 25% indicates diaphragm dysfunction.

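### State that the diaphragm factor is analysed as a continuous measure: section 4.1 with Appendix 8 reads as a yes/no factor, and section 10.3 leaves the form open

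*Combined protocol and SAP*

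**What the plan says.** - **Section 4.1, respiratory factors:** the diaphragm item is "Diaphragmatic dysfunction on admission to at Difficult-to-Wean Unit". No scale or coding is attached. The lung item beside it is named as a score.
- **Section 8.3:** "Ultrasound of the diaphragm will assess the excursion (mobility) and thickening of the diaphragm on the right and left".
- **Appendix 7, report form:** there are fields for thickening fraction in % and excursion in cm, right and left.
- **Appendix 8:** dysfunction is indicated by two thresholds. One is on excursion ("An excursion < 2.5 cm"), with a literature citation. The other is on thickening ("A TF < 25% indicates diaphragm dysfunction"), with no citation. There is no rule for combining the two measures or the two sides.
- **Section 10.3:** collected variables are compared between the success and failure groups by tests suited to their type. Those with p<0.20 go forward to a multiple logistic regression with AIC selection. On ultrasound it says: "The previously selected ultrasound variables will be included in the model predicting the success of decanulation". Neither the variables nor their form is named.
- **Section 10.1:** the sample size is "a necessary number of subjects of 100 patients", "based on an estimated 60% success of decanulation", with six variables in the final model.

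**The concern.** Read together, section 4.1 and Appendix 8 suggest that each patient will be coded as having dysfunction or not. On the thickening threshold alone, a patient at 24% would then differ from one at 26% but count the same as one at 5%. The values that separate these patients are already on the form.

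Lung and diaphragm ultrasound are the two examinations listed in section 8 as added by the research, and section 10.3 singles out ultrasound variables for the model. A weaker version of the diaphragm measure is more likely to fail the p<0.20 screen or to be removed by AIC. The study could then report no association with decanulation when the recorded values would have shown one. Because the form is not fixed, it could also be chosen after the data have been seen.

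**Working it through.** **1. The plan's own figure.** 6 variables × 10 events ÷ 0.60 = 100 patients, as in section 10.1. At 60% success this gives 60 successes and 40 failures.

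**2. Inputs.**
- From the plan: n = 100, 60:40 split, screen at p<0.20, significance level 5% (taken as two-sided; the plan does not say).
- Assumed, because the plan gives no figure: a normal measure with equal SDs, a true difference d of 0.4 to 0.7 SD, and a share q of 20% to 60% of all patients below the cut.
- Also assumed: one measure cut once, and all 100 patients classified as success or failure.

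**3. One setting by hand: d = 0.5, q = 0.30.**

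*Continuous.* The standard error is √(1/40 + 1/60) = 0.204 SD, so the expected z is 0.5/0.204 = 2.449.
- Screen: Φ(2.449 − 1.282) = Φ(1.167) ≈ 0.88.
- 5% test: Φ(2.449 − 1.960) = Φ(0.489) ≈ 0.69.

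*Dichotomised.* The cut that puts 30% of all patients below it gives 40.5% dysfunction among failures and 23.0% among successes (check: 0.4 × 0.405 + 0.6 × 0.230 = 0.300). The difference is 0.175.
- Null standard error: √(0.30 × 0.70) × 0.204 = 0.0935.
- Alternative standard error: √(0.405 × 0.595/40 + 0.230 × 0.770/60) = 0.0947.
- Screen: Φ((0.175 − 1.282 × 0.0935)/0.0947) = Φ(0.58) ≈ 0.72.
- 5% test: Φ((0.175 − 1.960 × 0.0935)/0.0947) = Φ(−0.09) ≈ 0.47.

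The loss in this setting is about 16 points at the screen and about 22 at 5%.

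**4. The grid by simulation.** 40,000 simulated studies per d, t-test on the value against uncorrected chi-square on the cut, with q = 20%, 30%, 50% and 60%:

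| d (SD) | Screen p<0.20: continuous → cut | Loss (points) | Two-sided 5%: continuous → cut | Loss (points) |
|---|---|---|---|---|
| 0.4 | 0.75 → 0.55-0.62 | 12.8-19.6 | 0.49 → 0.30-0.36 | 13.2-18.4 |
| 0.5 | 0.88 → 0.68-0.75 | 12.3-19.9 | 0.68 → 0.44-0.51 | 17.2-24.3 |
| 0.6 | 0.95 → 0.79-0.86 | 9.1-16.0 | 0.83 → 0.58-0.66 | 17.0-25.3 |
| 0.7 | 0.98 → 0.87-0.93 | 5.5-10.9 | 0.93 → 0.70-0.79 | 13.7-22.5 |

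Repeat runs move the ends by about a point. The normal approximation of step 3 reaches 20.7 points at the screen (0.751 to 0.544 at 0.4 SD, q = 20%). Rounded, the loss is about 5 to 21 points at the screen and about 12 to 26 at 5%. At 5% the normal approximation runs a few points higher, to about 29.

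**5. Share of information kept.** For a small shift in a normal measure, the relative efficiency of the cut is φ(z)²/[q(1 − q)], where Φ(z) = q. It is 0.49 at q = 20%, 0.58 at 30%, 0.64 at 50% and 0.62 at 60%.

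**6. Sensitivity.** Outside the assumed range the 5% loss varies widely. At d = 1.0 and q between 20% and 70% it is about 3 to 8 points. At d = 0.57 with only 10% of patients below the cut it is about 41 points.

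**The case against.** The strongest reply is that the documents never say the diaphragm will be analysed only as yes/no. The section 4.1 list names conditions more than codings: ICU-acquired weakness stands for an MRC score out of 60, and swallowing disorder for a 0-3 score. Section 9.2.2 marks several binary items as yes/no, and diaphragm ultrasound is not among them. Section 10.3 tests collected variables by type, and what the form collects is a percentage and a length. The plan as written therefore allows the continuous analysis. This stands. A reader might infer that the sponsor has committed to dichotomising, but the documents support only that yes/no is the natural reading and that the form is not fixed.

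Three further limits also stand.
- A reader might quote a single power loss as a property of this trial. The documents give no effect size, SD or prevalence of dysfunction, so every figure above is conditional. The 5% figures also overstate the loss at the plan's first selection step, which is p<0.20. At 0.7 SD the dichotomised factor still passes that screen 87% to 93% of the time.
- It is tempting to say the cut halves the information. That fits only a prevalence near 20%. Near the median the loss is closer to one third.
- The calculation cuts one measure once. Appendix 8 has two measures, section 8.3 has two sides, and section 10.3 does not say how patients who are never decanulated are classified. The actual binary factor could behave differently.

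It can also be said that section 7.7 uses absence or recovery of dysfunction in the decanulation decision, so a dysfunction factor matches bedside practice. That supports reporting it descriptively. It does not require the admission measurement to enter a regression as yes/no.

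**Conclusion.** The point holds as a conditional one: if the Appendix 8 cut-offs are used to build the factor, the analysis gives up information already on the form, and in every setting tabulated above the dichotomised version was the weaker. At 0.5 SD the chance of wrongly losing the diaphragm at the screen at least doubles, from about 12% to 25-32%.

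The size rests on normality, the 60:40 split, a difference of 0.4 to 0.7 SD and 20% to 60% of patients below the cut. Of these, only the 60:40 split (n = 100 at 60% success) comes from the plan. The point does not show that the planned analysis is wrong, since section 10.3 permits the better form. It is a cheap improvement, best settled before the data are analysed.

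**What to change.** In sections 4.1 and 10.3:
- State that the diaphragm factor on admission is analysed as a continuous variable, by t-test or Wilcoxon at the screen and as a linear term in the logistic model.
- Name one main measure, thickening fraction or excursion, and one value per patient across the two sides (for example the lower side).
- Add a linearity check.
- Count any second diaphragm measure against the six planned model variables, because entering both would use two of the six.
- Keep the Appendix 8 cut-offs for describing the cohort. If a binary form is kept in any analysis, state how the two cut-offs and the two sides combine.

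**Cost:** wording only, with no extra scan, patient or change in care. An odds ratio per unit is slightly harder to present than yes/no, and the linearity check is a small added step.
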